1.0 OBJECTIVES

This will be a multi-center, open-label, randomized study that directly compares the use of cyclosporine and plasma exchange to corticosteroids and plasma exchange as the initial treatment of patients with thrombotic thrombocytopenic purpura. This study has the following objectives:

Primary Objective

1.1 To determine if cyclosporine given individually as an adjunct to plasma exchange decreases the rate of exacerbation in patients with TTP compared to corticosteroids given as an adjunct to plasma exchange.

Secondary Objectives

1.2 To compare the CSA and PE treatment arm to the corticosteroid and PE treatment arm with respect to:

- exacerbation rate within 30 days post-PE
- clinical response rate
- number of exchange procedures to achieve clinical response
- relapse rate (recurrent disease >30 days after last PE)
- safety data for CSA as an adjunct to PE.
- the effects of corticosteroids vs. cyclosporine on ADAMTS13 antigen, activity, and ADAMTS13 antibody concentration and inhibitor titers using serial measurements both during and after discontinuation of study drug
- the VWF multimeric patterns after initial therapy and throughout longitudinal follow-up between the two treatment arms
- the laboratory biomarker(s) that are prognostic for TTP exacerbation and the risk of relapse

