5.4 ENROLLMENT/REGISTRATION OF PATIENTS

- 5.4.1 Patients must give written, informed consent prior to enrollment on this study. Informed consent may be obtained by the protocol chairman, the principal investigator at one of the additional sites, or one of their designees.

It is not uncommon for patients to have mental status changes related to their diagnosis of TTP (typically reversible with therapy) that may prevent them from being able to provide informed consent. If the principal investigator, co-investigator, or research study nurse do not feel the patient is able to provide informed consent, the study consent may be signed by the patient's legally authorized representative to enroll the patient in the study.

If the patient's legally authorized representative signs the consent, the patient must be then re-consented with the "re-consent form" if/when the patient regains the ability to provide informed consent.

- 5.4.2 Given concerns for the need to rapidly initiate, PE therapy should not be withheld while awaiting enrollment to this study. To allow sufficient time to evaluate for eligibility and obtain informed consent, patients will be permitted to be enrolled within 48 hours after the first PE procedure.

5.4.3 At the time of enrollment on this protocol, patients must be registered by phone with the study coordinating office at Ohio State University, the lead institution for this study. Contact information for all study personnel, protocol chairman, and co-investigators is detailed in section 15.0 of the protocol.

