6.0 Randomization of Patients

6.1 Patients will be randomized at the time of registration/enrollment on this clinical trial via contact with the study nurse/coordinator at the time of the initial registration of the subject. The study statistician ([name]) will conduct the randomization and relay this information to the study nurse who will be in contact with the treating/enrolling physician so that the appropriate medication (prednisone or cyclosporine) may be immediately started with PE.

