7.0 Treatment Plan: Initial Therapy

7.1 Therapeutic Plasma Exchange-Both Study Arms

7.1.1 Plasma exchange will be started as soon as the diagnosis of TTP has been made. (section 5.2.1). As it is important to institute therapy as soon as possible, patients will not have therapy delayed while obtaining informed consent.

7.1.2 Plasma exchange will be performed daily with one plasma volume exchanged using plasma as the replacement fluid until a complete remission is obtained (see response criteria 8.0).

7.1.3 Patients will receive either prednisone or cyclosporine orally as an adjunct to PE depending on the outcome of randomization (see sections 7.2-7.3 below). Therapy with these adjuncts will be initiated concurrent with and continue throughout plasma exchange therapy as described below.

7.1.4 After a complete remission (see response criteria 8.0) has been attained patients will have one exchange performed every other day for a total of 2 more exchanges, with the first day that the platelet count and LDH are normal counting as the first of the two exchanges.

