8.0 Clinical Response Criteria

8.1 Complete Remission

A patient will be deemed to be in remission if all of the following criteria have been met within 4 weeks from enrollment and maintained after the tapering of plasma exchange:

- platelet count $\geq 150,000$
- normalization of LDH
- a decreased or unchanged serum creatinine compared to the creatinine measurement obtained at the time of enrollment.
- clinical improvement in neurologic findings/deficits without the development of new neurologic findings/deficits by exam or radiographic studies.

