Additionally, we will evaluate several secondary clinical endpoints through this trial, including: 1) exacerbation rate within 30 days post-PE; 2) clinical response rate; 3) the number of PE procedures required to achieve a clinical response; 4) relapse rate; and 5) safety and tolerability of each of the adjuvant treatments to PE. Each of the rates will be calculated assuming that these endpoints are binomially distributed, and 95% confidence intervals generated. For the exacerbation rate endpoint, we will only include those patients who have achieved clinical response (i.e. excluding refractory patients) and compare these rates between the two arms. We will have at least 80% power to detect a difference if the true exacerbation rates are 55% vs. 90% for this subset analysis (not adjusting for multiple comparisons); however, this comparison is distinctly ancillary to our primary clinical interest of achieving treatment success in all patients treated versus only keeping responding patients from experiencing TTP exacerbation. We will also evaluate relapse as a time-to-event variable, where Kaplan-Meier methods will be used to assess time to relapse from last plasma exchange in responding patients. The number of exchange procedures required to achieve clinical response will be assessed between arms using Poisson regression. Safety and tolerability data will be summarized by type of adverse event with frequencies calculated and compared between arms. In addition to these planned quantitative analyses, we will also use graphical

analyses to assess patterns and differences in these factors between the treatment arms.

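### The start of the exchange count is not defined, and exchanges given before randomisation would pull the Poisson rate ratio toward 1

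*Combined protocol and SAP*

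**What the plan says.** Section 1.2 lists among the secondary objectives the "number of exchange procedures to achieve clinical response". Section 14.2 gives the analysis: "The number of exchange procedures required to achieve clinical response will be assessed between arms using Poisson regression". Neither place gives a starting point for the count, an offset or a covariate.

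Four other sections decide which exchanges could be counted:

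- Section 5.4.2: "PE therapy should not be withheld while awaiting enrollment to this study", and "patients will be permitted to be enrolled within 48 hours after the first PE procedure".
- Section 6.1: "Patients will be randomized at the time of registration/enrollment on this clinical trial".
- Section 7.1.2: "Plasma exchange will be performed daily with one plasma volume exchanged", until complete remission.
- Section 8.1: remission requires that its "criteria have been met within 4 weeks from enrollment and maintained after the tapering of plasma exchange", so the response window runs from enrolment and not from the first exchange.

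Section 7.1.3 says of prednisone and cyclosporine: "Therapy with these adjuncts will be initiated concurrent with and continue throughout plasma exchange therapy as described below". This does not fit a patient who is randomised a day or two after the first exchange.

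**The concern.** An exchange given before randomisation cannot be affected by the assigned drug. It is a baseline quantity with the same expected value in both arms. Poisson regression with its usual log link estimates a ratio of means, and adding the same expected amount to numerator and denominator moves that ratio toward 1.

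Fewer exchanges is part of the trial's rationale: section 2.4 expects effective immunosuppression to shorten the course of plasma exchange. With the start undefined, two analysts could follow section 14.2 faithfully and report different ratios, and the choice could be made after the data are seen. At stake are the interpretability and some of the power of one secondary comparison.

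**Working it through.** **Plan's own figure.** The plan gives no effect size or power for this endpoint, so there is nothing to reproduce.

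**Inputs**

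- Pilot median exchanges to remission: 6.5 with corticosteroids (section 2.6) and 5 with cyclosporine (section 3.2). They are used here as means, which is an assumption.
- Responders: 36 per arm (section 14.1) times pilot response of 11/12 and 10/12 gives 33 and 30. The average is 31.5, taken as 32 per arm.
- Two-sided alpha of 0.05. The plan states this for the primary test; it is assumed here.
- Prior exchanges per patient: 0, 1 or 2, equally likely, with the same distribution in both arms. This is an assumption, because the documents give no distribution.

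**Step 1: how many exchanges can precede randomisation.** With daily exchange at 0, 24 and 48 hours, a patient enrolled before the first exchange has none. Enrolment in the first day after it gives one, and enrolment in the second day gives two. Three needs enrolment at the very end of the window.

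**Step 2: effect on the estimate.** Let the post-randomisation means be mT and mC, and the mean prior count k in both arms.

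- Ratio from randomisation: mT/mC. Ratio from first exchange: (mT + k)/(mC + k), which is closer to 1.
- Difference: (mT + k) − (mC + k) = mT − mC, unchanged.

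**Step 3: numbers.** Take mT = 4, mC = 5.5 and k = 1 (the mean of 0, 1, 2), so that the totals equal the pilot figures of 5 and 6.5. Approximate power is Φ(|ln ratio|/SE − 1.96), with SE = √(1/(32·m1) + 1/(32·m2)).

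| Count starts at | Means | Ratio | Difference | SE | z | Power |
|---|---|---|---|---|---|---|
| Randomisation | 4 v 5.5 | 0.727 | −1.5 | 0.116 | 2.74 | 78% |
| First exchange | 5 v 6.5 | 0.769 | −1.5 | 0.105 | 2.50 | 70% |

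The second line slightly overstates the loss. It treats the total as Poisson, but a prior count uniform on 0 to 2 has mean 1 and variance 2/3. Simulating this scenario with model-based errors gave power of 76–79% from randomisation and 69–74% from first exchange, a loss of about 5 to 7 points. With robust errors it gave about 79% and 73.5%, a loss of about 5 points.

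**Step 4: if the pilot counts contain no pre-drug exchanges.** Then 5 v 6.5 are post-randomisation means: ratio 0.769, power about 70% with 33 and 30 responders. Adding a mean of one prior exchange gives 6/7.5 = 0.80 and about 63%. The direction is the same and the loss is about 7 points.

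**Step 5: if the prior count is the same for everyone.** With post-randomisation means of 3 v 4.5 and exactly two prior exchanges each, robust-error power was 87.3% from randomisation and 87.5% from first exchange, so nothing is lost. Model-based power fell from 87% to 75%, because the Poisson variance is too large for a count that contains a constant.

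**Step 6: no true effect.** With Poisson counts of mean 4.5 in both arms, model-based type I error was about 0.05 from randomisation and 0.02–0.04 with prior exchanges included. The ratio stayed at 1.00.

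**The case against.** The strongest reply is that the plan never says prior exchanges are counted. A reader might infer from section 14.2 that they are, but the start is undefined, and the enrolment-based window in section 8.1 points the other way. That stands: the defect is an undefined count, not a wrong one.

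Second, total exchanges is a legitimate endpoint. It measures exposure to plasma, which section 2.4 wants to reduce, and randomisation balances the prior part in expectation. This also stands, and it is why the total should still be reported. It does not settle which count the Poisson ratio refers to.

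Third, late enrolment may be uncommon. Forty-eight hours is a maximum, and sections 7.1.3, 7.2.1 and 7.3.2 describe the drug starting with exchange or at diagnosis. The documents cannot settle this, so the size is conditional.

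Two stronger inferences are tempting and fail:

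- A reader might say that the arm difference is diluted. Only the ratio is; the difference of 1.5 exchanges is the same under either count.
- A reader might subtract two exchanges from both pilot medians and conclude that the ratio should be 3/4.5 = 0.67, with power of 87% instead of 70%. Nothing says that the pilot counts include pre-drug exchanges; section 2.6 describes prednisone given alongside daily exchange. A constant of two in every patient removes no information, and that apparent gain comes from the Poisson variance (step 5).

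**Conclusion.** The point holds as a minor one. The start of the exchange count is undefined in sections 1.2 and 14.2, while sections 5.4.2, 6.1 and 7.1.2 together allow one or two exchanges, at the extreme three, before randomisation. Counted from the first exchange, they attenuate the rate ratio and cost some power.

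The illustrative size is a ratio of about 0.77 instead of 0.73 and a loss of about 5 to 7 points of power under model-based Poisson regression. With robust errors the loss lies between about 5 points and none, depending on how much the prior count varies between patients. These figures rest on medians used as means, about 32 responders per arm, Poisson counts after randomisation, and prior exchanges spread evenly over 0 to 2. If everyone is randomised at or before the first exchange, the effect is zero.

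The documents do not support a claim of false-positive risk from this source, or of any effect on the primary comparison of success rates, which does not use this count.

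**What to change.** In section 14.2:

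1. Define the endpoint as the number of exchanges from randomisation to clinical response.
2. Include the number of exchanges before randomisation as a baseline covariate. Patients randomised later may be nearer to response, and the covariate allows for that.
3. Use robust standard errors. They correct the variance mismatch in step 5. They also guard against overdispersion: with variance twice the mean and no true effect (mean 4.5 per arm), model-based type I error was about 0.16 even when counting from randomisation.
4. Report total exchanges from first exchange to response by arm, as treatment burden.

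Separately, reconcile the wording in section 7.1.3 on when the adjunct starts with the 48-hour window in section 5.4.2.

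The cost is a few sentences and one data item. The number of pre-enrolment exchanges must be captured; the documents do not say that exchange dates before enrolment are recorded, so this should be checked and not assumed. The main ratio will no longer describe total exchange burden, which item 4 covers.

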2.6 Clinical Outcome- Concurrent Corticosteroids and PE as Initial Therapy

A total of 12 patients with idiopathic TTP were treated with corticosteroids and PE. Patients received prednisone at a dose of 1 mg/kg/day concurrently with daily plasma exchange therapy which was continued until remission was achieved (platelet count $>150 \times 10^9/\text{ul}$). PE was then tapered and discontinued with the prednisone tapered over the next 4 weeks. Ten of 12 patients achieved remission after a median of 6.5 daily exchanges, but exacerbations of TTP occurred in 6/10 (60%), comparable to the 50% exacerbation rate from the Oklahoma Blood Institute where steroids were not routinely used. (Table 1) More importantly, there was no significant improvement in ADAMTS13 activity at remission nor suppression of the inhibitor measured within a week of tapering PE. Given these data, we then began to study alternative forms of immunosuppressive therapy as an adjunct to PE.

Table 1.
Clinical and Laboratory Data From Steroid and Plasma Exchange-Treated Patients

Clinical Data	
Remission	10/12
Med. Days to Remission	6.5 (range, 4 to 10)
Exacerbation Rate	6/10 (60%)
Laboratory Data	
Med. Pre-Treatment ADAMTS13	<1% (range, <1 to 5)
Med. Remission ADAMTS13	4% (range, <1 to 72)
Med. Pre-Treatment Inhibitor (ug/ml)	632 (range 188 to 3,574)
Med. Remission Inhibitor (ug/ml)	788 (range 144 to 8,113)

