3.1 Concurrent Cyclosporine and PE for Exacerbations and Refractory TTP

Ten patients with exacerbations or refractory TTP after their initial therapy received CSA concurrent with the resumption of PE.(48) All 10 patients were treated with concurrent CSA (2-3 mg/kg in a twice daily divided dose) and PE. CSA was continued for a total of 6 months and then discontinued. Nine of the 10 patients achieved remission after a median of 11 daily exchanges (range, 5-45), with only 1/9(9%) suffering an exacerbation after tapering PE. Median follow-up for the entire cohort is 31 months (range, 12 to 41). Eight of the 10 patients maintained a continuous remission throughout the planned 6 months of CSA and then discontinued therapy.

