8.2 Partial Response

8.2.1 Patients showing improvement (increase in platelet count and a decrease in the LDH, but not meeting the full criteria for complete remission) should continue concurrent CSA or prednisone and plasma exchange therapy for up to 4 weeks. If at that time patients still have not met the criteria for remission, patients will be considered to have been unable to achieve remission but will remain on this protocol for the purposes of data and clinical sample collection and for safety monitoring, but may be treated at the discretion of their treating physician.

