14.0 Statistical Analysis

14.1 Statistical Considerations-Sample Size Determination

For the study of the primary endpoint (treatment success rate), the sample size required is calculated based on the data from our previous publications. In these previous studies that looked separately at CSA/PE in 10 patients and at corticosteroids/PE in another 10 patients, we saw promising results that led to our hypothesis that CSA/PE treatment for TTP patients results in greater treatment response. In those studies, the primary endpoint was the proportion of patients who had TTP exacerbation, which is a more stringent endpoint that does not include other types of treatment failures such as refractory patients and/or death within 30 days post-PE. In the previous published pilot studies, we showed that 6/10 corticosteroid-treated patients exacerbated versus 0/10 CSA-treated patients. Combined with experience with subsequently treated patients, we observed an overall treatment success rate of 80% and 83% in refractory vs. de novo TTP patients, respectively, treated with CSA+PE versus 33% in those treated with corticosteroids+PE.

In terms of our primary endpoint of treatment success rate, we have designed a phase III trial that compares the proportion of treatment successes in each arm. Specifically, this study design will have at least 80% power to determine a significant difference in the treatment success rates between the arms if the true rates are 50% vs. 80%, assuming a significance level of 0.05 and a two-sided test. This reflects a clinically meaningful difference, and the data from our previous studies and experience support it as a feasible difference to detect. We plan to enroll a total of 72 patients to this trial (36 to each arm) to test the null hypothesis that there is no difference in treatment success rate between these treatments.

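### Section 14.2 compares exchanges to response by plain Poisson regression, with no allowance for dispersion and no rule for patients who never respond

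*Combined protocol and SAP*

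**What the plan says.** Section 1.2 lists "number of exchange procedures to achieve clinical response" among the secondary comparisons between arms. Section 14.2 gives its analysis in one sentence: "The number of exchange procedures required to achieve clinical response will be assessed between arms using Poisson regression". It names no dispersion check, quasi-Poisson or negative binomial model, or robust variance. The only addition is a general statement that graphical analyses will also be used.

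Section 14.2 restricts the exacerbation rate and the time to relapse to responders. It names no analysis set for the exchange count. Three parts of section 8 decide who can have a count:

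- Section 8.1 requires complete remission within 4 weeks of enrolment.
- Under section 8.2, partial responders "should continue concurrent CSA or prednisone and plasma exchange therapy for up to 4 weeks", and are then classed as not having reached remission.
- Under section 8.3, patients with no improvement after 1 week are refractory and have failed therapy.

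Section 8 does not say whether clinical response, the term used for this endpoint, means complete remission only or also partial response.

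**The concern.** The number of exchanges to response is a waiting time: daily exchange goes on until a stopping rule is met. Nothing in that process makes the variance equal the mean. If responders are homogeneous, the variance can be well below the mean, and the Poisson test is then conservative. If a few respond late, it can be well above the mean, and the test rejects too often. Plain Poisson regression adapts to neither case.

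The second gap is that a patient who never responds has no count. If such patients are simply left out, the arms are compared on subsets selected by outcome. If they are given a value, the result depends on which value. Left open, that choice could be made after the data are seen. Shorter courses of exchange are part of the stated rationale for immunosuppression (section 2.4), so this endpoint is likely to be quoted.

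**Working it through.** **The plan's own figures.** The documents give no mean, SD, dispersion or power for this endpoint. It inherits the trial's 36 per arm, which reproduces with unpooled variances: (1.96 + 0.8416)² × (0.50×0.50 + 0.80×0.20) / 0.30² = 35.8, rounded up to 36. The sample-size text describes its test as "assuming a significance level of 0.05 and a two-sided test", and the same level is used below.

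**Step 1: dispersion in the first-line data.** Section 2.6 reports: "Ten of 12 patients achieved remission after a median of 6.5 daily exchanges". Table 1 gives the range as 4 to 10. Every set of 10 whole numbers with that median and range was enumerated (244 sets), and φ = sample variance / mean was computed for each.

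- Smallest φ: 4, 6, 6, 6, 6, 7, 7, 7, 7, 10. Mean 6.6, variance 2.27, φ = 0.34.
- Largest φ: 4, 4, 4, 4, 4, 9, 10, 10, 10, 10. Mean 6.9, variance 9.43, φ = 1.37.

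The interval 0.34 to 1.37 contains 1. The first-line cyclosporine cohort (section 3.2: 11 of 12 responding, median 5) has no range, so it gives no bound.

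**Step 2: what φ does to the test.** For a nominal two-sided 5% Wald test with model-based Poisson standard errors, true error = 2 × [1 − Φ(1.96/√φ)].

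| φ | True error |
|---|---|
| 0.34 | 0.1% |
| 0.5 | 0.6% |
| 1 | 5% |
| 1.37 | 9% |
| 2 | 17% |
| 3 | 26% |

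**Step 3: a slow tail inside the 4-week window (assumption).** Let a share p of responders need 11 to 28 exchanges, uniformly: mean 19.5, variance (18² − 1)/12 = 26.9. Let the others have mean 6.5 and φ = 0.5, so variance 3.25. The means differ by 13, so the mixture mean is 6.5 + 13p and its variance is (1 − p)×3.25 + p×26.9 + p(1 − p)×13².

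- p = 0: φ = 0.5, error 0.6%.
- p = 0.05: mean 7.15, variance 3.09 + 1.35 + 8.03 = 12.46, φ = 1.74, error 14%.
- p = 0.10: mean 7.80, variance 2.93 + 2.69 + 15.21 = 20.83, φ = 2.67, error 23%.

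Simulating this mixture with no difference between arms (20,000 runs, 30 and 33 responders, fast group binomial with 13 trials and probability 0.5) gave these rejection rates:

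| Slow share | Poisson | Quasi-Poisson | Robust, uncorrected |
|---|---|---|---|
| 0 | 0.5% | 4.8% | 5.6% |
| 5% | 13.5% | 5.0% | 7.0% |
| 10% | 22.3% | 5.2% | 7.1% |

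In separate simulations without a mixture (mean 6.5, φ from 0.5 to 5), quasi-Poisson stayed between 4.5% and 5.5%, while Poisson ran from 0.6% to 37%.

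**Step 4: patients without a count.** Pilot non-response was 2/12 on steroids and 1/12 on cyclosporine (sections 2.6 and 3.2). Carried forward, 36 × 10/12 = 30 and 36 × 11/12 = 33 patients have a count, so 72 − 63 = 9 have none: 6 on steroids and 3 on cyclosporine.

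Suppose responders average 6.5 exchanges in both arms. The responders-only cyclosporine/steroid ratio is then 1.00. If non-responders are given a value v, the ratio is (11/12 × 6.5 + 1/12 × v) / (10/12 × 6.5 + 2/12 × v).

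- v = 7: 6.54/6.58 = 0.99.
- v = 28: 8.29/10.08 = 0.82.

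The documents give no v, so the answer depends on a rule that has not been written.

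**The case against.** The strongest reply is that the documents do not show the standard errors to be wrong. That is correct. The one usable first-line range is compatible with φ = 1, and at the lower end the Poisson test is conservative. The slow tail in step 3 is an assumption that no first-line figure supports.

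A reader might point to section 3.1, where nine of ten patients "achieved remission after a median of 11 daily exchanges (range, 5-45"), and infer severe over-dispersion. Nine whole numbers with that median and range need φ of at least 8.0, which gives about 49% error. The inference does not carry over. Those patients had exacerbations or refractory disease, while section 5.2.5 admits a patient with earlier TTP only after 30 days without treatment for it. A daily course of 45 exchanges would also overrun the 4-week limit in section 8.1 and count as non-response.

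A reader might also infer that the analysis drops the slowest patients. The plan does not say so. It names no analysis set for this count, and any omission would come from the endpoint's definition rather than from the Poisson model. Non-responders also include patients declared refractory at 1 week, who are not simply slow. Response rate is a separate secondary endpoint, and refractory patients count as failures in the primary one, so an arm that leaves patients without remission would show it there.

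What remains is that the plan relies on a variance assumption with no support and no safeguard, and leaves a foreseeable missing-value question open. Not knowing the direction of the error is no defence, because the remedy works in both directions.

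**Conclusion.** The point holds as a missing safeguard on a secondary endpoint. Plain Poisson regression is specified for a waiting-time count whose dispersion is unknown. On the first-line data the true error of a nominal 5% test could lie anywhere from about 0.1% to 9%. A modest slow tail would take it to about 14% to 22%. The first range rests on 10 patients' summary statistics. The second rests on the assumed 5% to 10% share, the assumed 11 to 28 exchanges and an assumed under-dispersed fast group. Which applies here cannot be known in advance.

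The handling of non-responders is a secondary part of the point. About 9 of 72 patients would have no count if the pilot rates carry over, and those rates come from only 12 patients per cohort. The primary comparison is not affected.

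**What to change.** In section 14.2:

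1. Keep the rate ratio from the Poisson model, but take standard errors, confidence interval and p-value from a quasi-Poisson fit (estimated dispersion, t reference). Robust standard errors with a small-sample correction would also serve; uncorrected ones rejected at up to about 7% above.
2. State which section 8 category counts as clinical response for this endpoint, and label the rate ratio as a responders-only result.
3. Add a supportive analysis of all randomised patients: cumulative proportion responding by exchange number, compared between arms. Patients who are refractory, die or have no remission by 4 weeks stay in the denominator throughout as never responding. They should not be censored when declared refractory or at death, because that would treat them as still able to respond. Exchanges given at the physician's discretion after refractory disease is declared then do not enter the count.

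The cost is a few sentences in the plan and slightly more reporting. No new data or patients are needed.
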